4.4.3 Intervention 1: Dialogue-Based Webinar

LTCWs will attend one-time virtual webinars in groups of no more than 20, scheduled at different times, and different days (including weekends). Each webinar will be led by a LTCW peer trained in SDM principles. It will also be co-facilitated by a physician with expertise in COVID-19 vaccination, and a communication expert with experience in SDM.

The webinar intervention agenda is as follows: i) the LTCW facilitator will introduce the session and go over important instructions, including the set of community standards, ii) the physician facilitator will review the COVID-19 vaccine Option Grid™ conversation aid (see Appendix A) and other related topics of interest using the principles of the SDM three-talk model⁴⁷. A link to the online Option Grid™ will also be sent to participants prior to their webinar commencing iii) participants will then be presented with the four major content topics pertaining to COVID-19 and the vaccines (consistent with those listed above in section 4.4.2) and will vote (via a poll) on the two content topics that matter most to them. The physician facilitator will then start by answering questions from participants related to the top voted content areas, and then open questioning up to all topics until there are no remaining queries. The webinars will end with the LTC resident video described earlier.

Throughout the webinars, the communication expert will assist with any related discussions where needed and respond to study-related questions/issues or technical troubleshooting. Webinar durations will vary, running up to 1 hour, or less if there are no remaining questions. Participants will also be invited to join a facilitated online discussion in the webinar chat and their engagement will be monitored (e.g., number of chat messages posted during each webinar and webinar content).

A dialogue-based webinar refresher will also be delivered to all participants in this arm one week prior to their T2 survey invitation (see Figure 2). The refresher will be a pre-recorded webinar (video and audio-only versions) lasting ~20 minutes, sent to participants via email. The structure of the recorded webinar will closely resemble that of the primary intervention, and will include a review of the COVID-19 Option Grid™, question and answer discussion, and LTC resident video. It will be available to participants as a video and an audio-only recording.

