We will partner with the National Association of Health Care Assistants (NAHCA) to recruit 1800 LTCWs. Eligible LTCWs will self-identify as: 1) being at least 18 years old, 2) living in the United States, 3) having worked in a long-term care setting in the past two years, 4) able to verify their LTCW status, 5) not currently be pregnant or breastfeeding, and 6) able to read, write, and understand English, and 7) being at least somewhat worried about the COVID-19 vaccines and/or not having received any COVID-19 booster vaccine. Contingent on study results, in the sustainability phase (see Figure 3), we will open the materials to other LTCWs.

Interventions: We selected two interactive interventions with our stakeholder partners, based on provisional evidence of their effectiveness and Peretti-Watel's vaccine hesitancy framework. Interventions will be co-designed and adapted with LTCWs and the Institute for Healthcare Improvement (IHI) co-investigators. We will include an enhanced usual practice arm.

Arm 1: Dialogue-Based Webinars

Six hundred LTCWs will attend virtual dialogue-based webinars in groups of 20. An existing COVID-19 conversation aid (English version) will be available to all participants. Each webinar will be co-facilitated by a LTCW and physician expert, and assisted by a communication expert.

Arm 2: Social Media Website

Six hundred LTCWs will be invited to visit a curated COVID-19 social media website, co-designed with LTCWs and NAHCA. The site will be interactive, dynamic, and have multi-component content derived from LTCW-nominated platforms, e.g., Facebook, YouTube, etc. It will address frequent concerns and topics that are deemed relevant by LTCWs.

Arm 3: Enhanced Usual Practice

Six hundred LTCWs will be directed to visit the COVID-19 vaccine information on the CDC website.

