4.1.2 Randomized Controlled Trial (Aims 1 and 2)

The randomized controlled trial will have three arms, with randomization at the individual person level. Arm 1 is a dialogue-based webinar intervention. Arm 2 is a social media website intervention. Arm 3 is enhanced usual practice. Intervention and comparator arms are described in detail in section 4.4. We will use online and in-person recruitment strategies to enroll 1,800 LTCWs to the trial. Trial data will be obtained primarily via four self-reported participant surveys, delivered to each participant over a period of approximately six months (Figure 2). We will also collect online activity data in each intervention arm. In the trial set-up period, an additional online survey will be administered to a sample of ~500 people from the general population who are demographically representative of LTCWs, to test novel trial screening questions (e.g., COVID-19 vaccine concerns) and adapted outcome measures (e.g., vaccine confidence), and help refine the content of the interventions.

Figure 2. CONSORT Study Flow Diagram

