4.6 Sample Size and Power Calculation

Using historical Vaccine Confidence Index (VCI) data⁷⁰ and current vaccination rates⁷¹, a VCI threshold was determined that was significantly correlated with rates of vaccination ($p=0.0001$). Assuming the analytic approaches outlined in sections 4.7.2 and later, the sample size of 1,800

LTCWs (600 per arm) provides 80% power to detect an 8% difference in the rate of scores above this threshold between groups with a two-sided test at type I error rate of 0.05. The sample size is sufficient to retain 80% power to detect a 10% difference (assuming outcomes are randomly distributed across retained and lost subjects) after 40% attrition.

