4.7.3 Allocation of Interventions

We will use the randomizer function built into the online Qualtrics survey platform to allocate participants to a trial arm and associated intervention. At the very end of the T0 Survey, the Qualtrics survey platform will automatically generate participants' trial arm and they will be presented with basic information pertaining to their assigned intervention at that time. A 1:1:1 allocation ratio will be used. After submitting their survey, those randomized to Arm 1 (Dialogue-Based Webinar) will be automatically redirected to a separate Qualtrics survey where they can sign up for one of several pre-scheduled webinar sessions. Those randomized to Arm 2 (Social Media Website) will be automatically redirected to the Social Media Website. In order

to access website content, they will first be required to create a username and password for the site. Those randomized to Arm 3 (Enhanced Usual Practice) will be automatically redirected to a specific page(s) on the CDC website (<https://www.cdc.gov/coronavirus/2019-ncov/vaccines/index.html>).

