4.9 Data Management

4.9.1 Data Management Plan

Collecting data. The primary source of trial data will be collected via online surveys administered to recruited study participants. We will also use activity data from the social media website and associated analytics software (Google Analytics and Google Cloud Platform), (b) Zoom webinar content/recordings and registration and attendance data, and (c) user-entered or participant-generated data from Salesforce. Data from Aim 3 interviews will be collected via audio recordings and subsequently transcribed by a transcription company (Civicom, Inc.). Table 4 below details all platforms and organizations that will receive study data during the trial, and which data they will receive.

Table 4. Data platforms and data received

Location	Description of Data Received
Qualtrics (Participant survey portal)	All participant survey data (e.g., screening and consent information, contact information, participant characteristics, and primary and secondary study outcomes).
Salesforce (Participant management; data will automatically flow in from Qualtrics and Zoom)	Participant information flowing from Qualtrics/Zoom includes contact information, characteristics, vaccine and booster status, trial arm assignment, Zoom registration, and survey metadata (e.g., completion date, unique study ID). Data will also be generated in Salesforce by research team members' manual entry of information (e.g., call logs) or participant-generated information (i.e., response to a text message sent from within Salesforce).
Mogli/Telnyx (Integration for Salesforce that supports text messaging)	Participants' first name, cell phone number, and study-related messaging (includes unique links to surveys and interventions).
ActiveCampaign (Email marketing software for sending intervention refreshers)	Participants' first name, last name, email address, and study-related messaging.
Zoom (Includes Panopto for Zoom video storage)	Participants' name, email address, meeting registration, meeting attended, time joined and left meeting, chat logs, meeting recordings (audio and visual, including participant faces if they choose to show their video).
Social Media Website (WordPress site that will be hosted on a Dartmouth College server)	Participants' name, username and password, email address, and any other information related to their website engagement.

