P-values ≥ 0.0001 will be reported to 4 decimal places; p-values less than 0.0001 will be reported as " <0.0001 ". The mean, standard deviation, and any other statistics other than quantiles, will be reported to one decimal place greater than the original data. Quantiles, such as median, minimum, or maximum will use the same number of decimal places as the original data. Estimated parameters, not on the same scale as raw observations (e.g. regression coefficients) will be reported to 3 significant figures.

Adherence to interventions

Analysis of both intention-to-treat (ITT) and as-treated populations will be performed. All participants who are randomized to a trial arm will be included in the ITT analyses. Participants who adhere to major engagement criteria for their primary intervention will be included in the as-treated analyses.

Analysis methodology

Aim 1

To compare the impact of two interventions delivered online: 1) a dialogue-based webinar (webinar) using the existing COVID-19 Option Grid conversation aid and, 2) an interactive and, dynamic, and multi-component social media web application (social media website), compared to enhanced usual practice (link to Centers for Disease Control (CDC) vaccine website), on COVID-19 vaccine confidence (primary outcome), and other secondary outcomes among LTCWs. We hypothesize that each intervention will be superior to enhanced usual practice at increasing vaccine confidence (*Hypothesis 1.1*) and that the dialogue-based webinar intervention will be superior to the social media arm at increasing vaccine confidence (*Hypothesis 1.2*).

Corresponding analyses

Primary outcome

The primary outcome is the binary classifier of vaccine confidence derived from the three-item Vaccine Confidence Index (VCI), evaluated at 3 weeks post-randomization, which will be analyzed by randomization arm. The determined binary predictors of intervention outcomes will be compared using two-proportion z-tests to identify significant differences between each intervention and enhanced usual practice (Arm 1 vs Arm 3 & Arm 2 vs Arm 3 - superiority analyses) and between the intervention arms (Arm 1 vs Arm 2 - two-tailed equivalency analysis).

Secondary outcomes

- *Change from baseline in COVID-19 Vaccine Confidence.* Analysis of change from

baseline will be based on a binary classifier whether the average score increases (1) or does not increase (2) at T1, T2, and T3 versus baseline.

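### The primary z-tests ignore webinar sessions, so both Arm 1 comparisons have standard errors that are too small if sessions differ in effect; the error is probably small under intention to treat

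*Combined protocol and SAP*

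**What the plan says.** Participants are randomised individually: section 4.1.2 specifies three arms "with randomization at the individual person level", and section 4.7.3 adds that "A 1:1:1 allocation ratio will be used". Arm 1 is then delivered in groups. The abstract plans that "Six hundred LTCWs will attend virtual dialogue-based webinars in groups of 20", and section 4.4.3 sets 20 as a ceiling: "LTCWs will attend one-time virtual webinars in groups of no more than 20". After randomisation, Arm 1 participants sign up for one of several scheduled sessions (section 4.7.3).

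Within a session the group votes on which topics come first, asks its own questions and uses a shared chat, and the length varies (section 4.4.3). Section 4.1.4 expects sessions to differ: webinars are to be picked for process evaluation by size, duration, richness of exchange, conflict and early departures.

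In Appendix B, the primary outcome at 3 weeks "will be compared using two-proportion z-tests to identify significant differences between each intervention and enhanced usual practice", and the two intervention arms are compared in the same way. No session term appears. Section 4.6 mentions no ICC or design effect. The multiple-testing section of Appendix B sets cut-offs of 2.15 and 2.45 standard errors but does not change how the standard error is computed. The only mixed-effects model is for moderation and names no session effect. The data clustering in section 4.8.2 is an exploratory search for groupings of participants.

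The session attended will be known. Table 4 in section 4.9.1 lists "meeting registration, meeting attended, time joined and left meeting" among the Zoom data, and section 4.8.3 links Zoom data to the survey data by participant.

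**The concern.** People who share a live discussion also share whatever made that discussion more or less persuasive. If that varies between sessions, the Arm 1 proportion is more variable than the binomial formula allows. Arm 3 has no such grouping, so the data are partially nested: clustered in one arm and independent in the comparator.

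Two of the three primary tests involve Arm 1, the arm hypothesised to be best. With a standard error that is too small, the 0.016 threshold per test is not the error rate achieved, intervals for the Arm 1 effects are too narrow, and the power in section 4.6 is optimistic for those contrasts.

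For secondary outcomes less is at stake. Appendix B sets no significance threshold for them and reads them as trends, so only the width of their intervals is affected.

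**Working it through.** **The plan's own figure.** Section 4.6 states that 1,800 "LTCWs (600 per arm) provides 80% power to detect an 8% difference in the rate of scores above this threshold between groups", for a "two-sided test at type I error rate of 0.05". No control rate is given. Taking 46% vs 54%, close to the least favourable case:

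- null SE = √(2 × 0.5 × 0.5 / 600) = 0.02887
- alternative SE = √(2 × 0.46 × 0.54 / 600) = 0.02878
- (0.08 − 1.96 × 0.02887) / 0.02878 = 0.81, so power is 79.2%

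At 40% vs 48% power is 79.8%, and at 30% vs 38% it is 83.4%. The stated 80% is therefore reproduced by a calculation that treats all observations as independent.

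**Inputs for the check.**
- From the documents: sessions of at most 20; 600 per arm; attrition of 40% considered in section 4.6, which leaves 0.6 × 20 = 12 analysed from a full session; cut-offs of 2.15 SE (one-sided, Arm 1 vs Arm 3) and 2.45 SE (two-sided, Arm 1 vs Arm 2).
- Assumed: ICC 0.01 to 0.05, meaning correlation created by the session. Section 4.4.2 reports low early webinar attendance without a figure, so one case takes half of Arm 1 attending in sessions of 10, with 0.6 × 10 = 6 analysed.

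Arm 1 vs Arm 2 is labelled an equivalence analysis but has no margin, so it is treated here as a two-sided test of difference.

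**Formulas.** With a = share of the analysed arm that attended and m = analysed members per session:

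- Arm 1 variance inflation: VI = 1 + a(m − 1) × ICC
- SE inflation of the difference, equal arms: f = √((VI + 1) / 2)
- actual error: P(Z > 2.15/f) one-sided; 2 × P(Z > 2.45/f) two-sided

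With independence, f = 1 and the errors are 0.0158 and 0.0143.

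**Example.** For a = 0.5, m = 6, ICC = 0.05: VI = 1 + 0.5 × 5 × 0.05 = 1.125; f = √(2.125/2) = 1.031. The one-sided error is P(Z > 2.086) = 0.0185 and the two-sided error is 2 × P(Z > 2.377) = 0.0175.

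| Case | ICC | VI | f | One-sided | Two-sided |
|---|---|---|---|---|---|
| Half attend, 6 analysed | 0.01 | 1.025 | 1.006 | 0.0163 | 0.0149 |
| | 0.02 | 1.050 | 1.012 | 0.0169 | 0.0155 |
| | 0.05 | 1.125 | 1.031 | 0.0185 | 0.0175 |
| All attend, 12 analysed | 0.01 | 1.110 | 1.027 | 0.0182 | 0.0171 |
| | 0.02 | 1.220 | 1.054 | 0.0206 | 0.0200 |
| | 0.05 | 1.550 | 1.129 | 0.0285 | 0.0300 |
| All attend, 20 analysed | 0.01 | 1.190 | 1.046 | 0.0200 | 0.0192 |
| | 0.02 | 1.380 | 1.091 | 0.0244 | 0.0247 |
| | 0.05 | 1.950 | 1.214 | 0.0383 | 0.0437 |

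A beta-binomial simulation of the last case (40,000 runs, one-sided nominal 0.016) gave 0.020, 0.024 and 0.038, in agreement with the formula.

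**Family-wise bound.** The sum of the three primary tests, with Arm 2 vs Arm 3 fixed at 0.0158, is 0.0158 + 0.0158 + 0.0143 = 0.0459 under independence. At ICC 0.01 to 0.05 it becomes 0.047–0.052 (half attend), 0.051–0.074 (12 analysed) and 0.055–0.098 (20 analysed), against the intended 0.050.

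**As-treated.** Removing non-attenders sets a = 1. With 6 analysed per session, VI becomes 1 + 5 × ICC = 1.05–1.25, twice the excess variance of the first case. With equal arms f is 1.012–1.061 and the errors are 0.0169–0.0213 and 0.0155–0.0209. If the as-treated Arm 1 is smaller than its comparator, it carries more of the variance and f is larger.

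**Power of a correctly sized test.** Multiplying both SEs by f, at two-sided 0.05:
- 600 per arm, 46% vs 54%, all attending in 20s: 79.2% falls to 75.5%, 72.0% and 62.7% at ICC 0.01, 0.02 and 0.05.
- 360 per arm, 46% vs 56%, half attending with 6 analysed: 76.7% falls to 76.1%, 75.6% and 74.1%.

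**The case against.** The strongest reply is that sharing a session does not by itself make the z-test wrong. Participants are randomised individually and then choose a session. If like-minded people pick the same session, their answers will be correlated, but the variance of the arm mean is unchanged. Only dependence that the session creates matters, and if the webinar changes nobody's view the z-test keeps its error rate. This stands. The error rates above therefore describe session effects that vary around an average of zero. The standardised agenda, Option Grid, topic list and closing video may also keep session effects small.

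The second reply is about size. The largest figures need every Arm 1 participant to attend, every session to be full and nobody to be lost by 3 weeks. Section 4.4.2 already reports low attendance. In the half-attending case the SE is understated by 0.6% to 3%, and the two-sided error stays below 0.016 at ICC 0.01 and 0.02 because the 2.45 cut-off is slightly strict. This also stands for intention to treat. It does not cover the as-treated analysis, where few unclustered non-attenders remain to dilute the effect.

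A reader might infer that outcomes within a session are necessarily correlated, or that the Arm 1 tests run at two to three times their nominal error. The documents support neither. They give no ICC, attendance rate or achieved session size, and the second reading takes the upper bound as the expected case.

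Arm 2 users also share comments and ambassadors. That is one open site with no separate sessions, so it offers no comparable cluster to adjust for.

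**Conclusion.** The omission is certain; its size is not. Arm 1 is delivered in groups whose content depends on the group, and neither the primary tests nor the power statement allow for this. If sessions differ in effect, the standard errors of Arm 1 vs Arm 3 and Arm 1 vs Arm 2 are too small.

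For ICC 0.01 to 0.05, an assumption, the low-attendance case is nearest to what the protocol reports and the distortion there is slight. Full attendance with 40% loss gives 0.0182–0.0285 one-sided and 0.0171–0.0300 two-sided. Full sessions of 20 without loss are an upper bound within that ICC range. The matter deserves a change in the SAP because it touches two of the three primary tests and can be settled with data already being collected. It does not show that the primary conclusions would be invalid.

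**What to change.** In Appendix B, for Arm 1 vs Arm 3 and Arm 1 vs Arm 2, in both the intention-to-treat and as-treated analyses:

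- Keep the difference in proportions, with cluster-robust standard errors and a small-sample correction. The cluster is the Zoom session attended; non-attenders and all Arm 2 and Arm 3 participants are singletons.
- Report the estimated session ICC with the number and size of sessions, noting that it may partly reflect self-selection.
- Keep the plain z-test as a sensitivity analysis.
- Use the same standard errors for secondary-outcome intervals involving Arm 1.
- Note in section 4.6 that the stated power assumes independent observations, and show it for a range of ICCs.

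A random-effects logistic model should not be offered as equivalent. It replaces the marginal difference in proportions with a conditional odds ratio, and a random-effects fit can give non-attenders more weight per person than session members. Either changes what is being estimated.

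The cost is SAP wording and modest programming; no new data are needed. Arm 1 intervals widen, power for its contrasts falls somewhat below the independent-observations figure, and robust errors may be slightly conservative if people self-select into sessions. The change should be fixed before outcome data are analysed, so that the choice of standard error is not made after seeing results.

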4.4.4 Intervention 2: Social Media Website

LTCWs will be invited to visit a social media website. The website is curated with popular and topical posts from social media platforms such as Facebook, TikTok, and YouTube that are made by medical experts, LTCWs, and other creators. The content and topics addressed on the website are dynamic in nature, with two new posts added daily.

The top of the website homepage features the four major content topics pertaining to COVID-19 and the vaccines (consistent with those listed above in section 4.4.2). Participants can navigate the website by selecting from these major topics, selecting subtopics listed in the sidebar menu or as hashtags assigned to each post, or by scrolling the remainder of the homepage (organized as an infinite scroll of all posts, sorted by most recently uploaded). The website supports participant interaction with features such as reactions and comments. Participants also receive email notifications when other users react or reply to comments they have made.

Three special website users affiliated with the study team who have worked as CNAs in LTC settings contribute to the website as ‘Community Ambassadors’. Their role is to promote user engagement by reacting and replying to posts and participants’ comments based on their own experiences as CNAs. Ambassadors also provide factual information on COVID-19, the vaccines, and boosters should participants ask any direct questions.

A social media website refresher will also be delivered to all participants assigned to this arm one week prior to their T2 survey invitation (see Figure 2). The refresher will be an email with previews and links (back to the full post on the social site) to a selection of featured website content.

